1.2.4. Modifications from the Statistical Section in the Final Protocol

The summary of modifications is listed in the following table.

Item	Protocol Section	Description
1	2.3 Exploratory Objective To assess medical visits/hospitalizations for abdominal pain or pancreatitis, medical visits/hospitalizations for pancreatitis, and medical visits/hospitalizations for cardiovascular disease	SAP Section 1.2.3: Modified exploratory objective for medical visits/hospitalizations to remove medical visits because it is not captured in e-CRF (consistent across all evinacumab studies).
2	2.3 Exploratory Objective	SAP Section 1.2.3, added two objectives: 
• To evaluate changes in the number and percentage of stomach pain, pain and abdominal symptom-free days, defined as the number and percentage of stomach pain free days, number of pain free days, and the number of abdominal symptom free days, as assessed by the HAP-SS.• To evaluate changes in the number and percentage of days where meals are avoided as assessed by the HAP-DB.
3	10.3.2 Safety Analysis Set The safety analysis set (SAF) includes all randomized patients who received any randomized study drug; it is based on the treatment received (as treated). Treatment compliance/administration and all clinical safety variables will be analyzed using the SAF.	SAP Section 3.2 and 3.3: Safety Analysis Set was divided to double-blind and single-blind period to be consistent with other evinacumab studies.
4	10.4.3.1 Primary Efficacy Analysis 
• “For the assessment of probability (computed from the likelihood function based on the observed data, which is equivalent to Bayesian posterior probability with uninformative prior) that mean TG percent change $\geq 40\%$...”• “A natural log transformation will be applied to the TG levels prior to	SAP Section 5.7.1: 
• For this proof-of-concept trial, estimates in TG change will be reviewed for 40% reduction supporting future drug development planning i.e., body of evidence review. Due to a lack of historical data in this indication, the application of posterior probability is not informative.• To provide further clarification, TG baseline definition was changed to the

	
analysis.”
 
“To reduce variability of TG baseline measurements, baseline at week 0 for patients randomized to active treatment is the geometric mean of the last 2 measurements during the placebo run-in (day -28, day -14) and week 0.”
	mean (arithmetic), since the log-transformed geometric mean of measurements is equivalent to the arithmetic mean of log-transformed measurements.
5	10.4.3.2 Secondary and Exploratory Efficacy Analysis	
SAP Section 5.7.2, 5.9 to 5.12:
 
Analyses for each secondary and exploratory endpoint are specified in the corresponding sections for each endpoint.The statement that “Continuous secondary and exploratory endpoints will be analyzed similarly to the primary endpoint” was deleted since for some continuous variables MMRM model may not converge due to the small number of visits/observations
6	10.4.5.3 Treatment Exposure The duration of exposure during the study will be presented and calculated as: (Date of last evinacumab injection - date of first evinacumab injection) + 24 weeks (length of follow-up period)	
SAP Section 4.6:
 
Duration of exposure was divided to double-blind and single-blind period and the duration definition was changed to “...+28 days/7” to be consistent with other evinacumab studies.

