10.4.3.2. Secondary and Exploratory Efficacy Analysis

Continuous secondary and exploratory endpoints will be analyzed similarly to the primary endpoint, except PP will not be computed. Binary endpoints will be summarized by counts and percents. Triglyceride mean percent change from baseline at each observation week will be summarized. Triglyceride mean percent change from baseline at each observation week will be analyzed and estimated for genetic mutations affecting LPL function (eg, homozygous LPL null [total LOF], heterozygous LPL null, with no LPL null gene mutations subgroups).

For the FDG-PET endpoint, comparisons will be within the evinacumab-treated patients in the double-blind period (week 12 vs week -2 for post/pre) and between the treatment groups in the double-blind period (week 12 vs week -2 for evinacumab in comparison to week 12 vs week -2 for placebo). In order to yield corresponding results, the MRI readout will be analyzed similarly as the FDG-PET endpoint. In addition, combining all evinacumab post/pre observations from the double-blind period (week 12 vs week -2) and the single-blind post/pre (week 24 vs week 12) for the patients who received placebo in the double-blind period, and post/pre (week 24 vs week -2 and week 24 vs week 12) for patients randomized to evinacumab during the double-blind period.

Summary statistics may be computed for time points beyond week 12 for the TG and continuous and exploratory endpoints in the patients randomized to evinacumab.

Summary statistics will be computed for the End of Day symptom diary and the symptom and dietary impact measure. These measures will also be psychometrically analyzed; this will be outlined in a separate psychometric analysis plan.

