1.2.2. Secondary Objectives

The secondary objectives of the study are:

- To determine the percent change from baseline in TG levels following 2 to 24 weeks of repeated IV doses of evinacumab overall and in subgroups with homozygous or compound heterozygous LOF mutations, heterozygous LOF mutations, and without LOF mutations in genes in the LPL pathway
- To assess changes in patient reported abdominal and gastrointestinal (GI) symptoms, dietary habits, and symptom/dietary impact measures
- To assess the degree of pancreatic injury/inflammation through 18F-2-Fluoro-2-Deoxy-D glucose positron emission tomography (18F-FDG-PET) imaging at baseline (placebo run-in) and change from baseline following 12 weeks of treatment with evinacumab as assessed by 18F-FDG standardized uptake values SUVmax and SUVmean
- To assess the degree of pancreatic injury/inflammation through diffusion weighted-magnetic resonance imaging (DW-MRI) at baseline and the change from baseline following 12 and 24 weeks of treatment with evinacumab as assessed by apparent diffusion coefficient (ADC)
- To evaluate the total evinacumab and total ANGPTL3 concentrations, and treatment-emergent anti-drug antibody (ADA) incidence during the evinacumab treatment and follow-up periods
- To evaluate the safety and tolerability of evinacumab

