5.7.1. Analysis of Primary Efficacy Variable

The primary efficacy analysis will assess within-patient percent change in TG over 12 weeks of evinacumab treatment (double-blind period for patients randomized to evinacumab and single-blind period for patients randomized to placebo).

The point estimates of TG percent changes between the placebo period and each observation week will be calculated using a Mixed-effect Model for Repeated Measures (MMRM) method in the FAS population. A natural log transformation will be applied to the TG levels prior to

analysis, aiming to provide a relatively normal data distribution (residuals will be examined for normality prior to proceeding with the analysis). The MMRM model will assess within-patient treatment comparisons (using an unstructured covariance matrix), while accounting for baseline TG, study visit, and baseline TG by study visit interaction. Note that study visits will be adjusted to start of evinacumab in order to pool data from both randomized groups of patients for this analysis. Since the comparison of study visits yields the within-patient comparisons of study treatments (ie, week 12 [after 12 weeks of treatment with evinacumab] compared to baseline at week 0 [after 4 weeks of treatment with placebo] for patients randomized to evinacumab and week 24 [after 12 weeks of treatment with evinacumab] compared to baseline at week 12 for those randomized to placebo), contrast and estimate statements will be used to assess treatment effects (least squares [LS] means with confidence intervals) and comparisons (LS mean ratio with CI). Within-patient comparisons will include all patients. In the event the MMRM model covariance matrix does not converge or normality is not achieved with the natural log transformation, then other transformations will be explored, including ranks.

To reduce variability of TG baseline measurements, baseline at week 0 for patients randomized to active treatment is the mean of the 3 log-transformed measurements at day -28, day -14, and week 0. Baseline at week 12 for patients switching from placebo to active is the mean of 3 log-transformed measurements at weeks 6, 8, and 12. Additional exploratory analyses may be carried out using the average of all available TG observations prior to first dose of active treatment, if no trend over time in those measurements is discernable.

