5.7.2. Analyses of Lipids Variables

Descriptive statistical analyses for the lipids defined in Section 4.7.2 will be summarized by treatment group and overall for the study, as well as by treatment group and overall within each cohort in the FAS population.

For descriptive summaries, percent change, and/or when appropriate, absolute change from baseline in conventional (US) and international units will be provided for lipids (LDL-C, Apo B, total-C, TG, non-HDL-C, Lp(a), Apo CIII, Apo A-1, and ratio Apo B/Apo A-1) at each protocol scheduled time point (as defined by e-CRF visit label) for each treatment group. For TGs, measurements on not-fasting patients will be excluded. Observed lipid values will be used, ie, imputation of missing values is not planned. For the evinacumab treated group, within-patient testing of endpoints with a non-normal distribution will use the Wilcoxon signed-rank test and endpoints with a normal distribution will use the paired t-test to evaluate the mean differences between baseline and each protocol visit. The p-value will be provided for descriptive purposes only.

Figures will be produced to support the summary tables for percent change and/or when appropriate absolute change from baseline. The plot will contain mean percent change +/- standard error (SE) through the study visits for each lipid variable (except TG and Lp(a)) by treatment group. For TG and Lp(a), plots will contain the median percent and /or absolute change from baseline along with quartiles (Q1 and Q3) over time by treatment group.

In addition, all lipids measurements (scheduled and unscheduled) will be included in patient listing.

During the SBTP, efficacy variables will be explored through descriptive statistics at each protocol scheduled visit for the total patients administered single-blind study treatment (total), as well as by the patient subgroups of study treatment received in the double-blind treatment period (i.e., evinacumab, placebo). Descriptive statistics will include the observed values of the same parameters as described for each variable in the DBTP, for patients in the single-blind safety analysis set.

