For patients receiving evinacumab in the DBTP, a combined summary including both the DBTP and SBTP assessments may be considered, referencing the double-blind baseline for variable calculations. Prolonged time between last dose of double-blind treatment and first dose of single-blind treatment will need to be taken into consideration when combining longitudinal efficacy data. Descriptive statistics will include the observed values of the same parameters as described for each variable in the DBTP, for patients in the double-blind safety analysis set.

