12. Lipids and lipoproteins, total cholesterol, LDL-C, HDL-C, TG, APOB, APOA1, and Lp(a) will be measured except at visit 1 and 1b.
13. At visit 1 and visit 1b, only total cholesterol, LDL-C, HDL-C, and TG will be measured.
14. Lipoprotein lipase level enzyme activity will be measured in fasting plasma collected at visit 2 only after eligibility has been confirmed by screening procedures at visit 1 and visit 1b.

15. Questionnaires should be completed daily for 7 days prior to each visit except for visit 3 (to be completed daily for the duration between visit 2 and visit 3).
16. Patients should be reminded by phone call 1 week prior to their visit to complete questionnaires.
17. Electrocardiogram should be performed before blood is drawn during visits that require blood draws.
18. In addition to assessment of adverse events at each visit, investigators should also ask patients if they have had any changes in abdominal symptoms and/or medical clinic visits for abdominal symptoms.
19. Confirm required contraception use and pregnancy status of female patients of childbearing potential and female partners (of child-bearing potential) of male patients will be monitored at clinic visits and by phone call for 24 weeks post the last dose of study drug. Women of childbearing potential will be provided urine pregnancy tests with instructions to test for pregnancy on days corresponding to phone call visits or Q4W if patients do not attend regularly scheduled visits.
20. Imaging may be performed up to 1 week prior to the visit and may be on the same day of the visit (for visit 3, MRI can be done on the same day or up to 4 days after visit 3). If done on the day of the visit, vital signs, ECG and blood draws after an 8-hour fast should be completed prior to the imaging procedures. Imaging procedures should be performed prior to study drug infusion.
21. PK samples will also be used for the analysis of total ANGPTL3.
22. In addition to the PK sample collected prior to drug administration, a PK sample should be obtained immediately after the end of each infusion.

Signature Page for VV-RIM-00078988 v1.0

[figure not shown]
ESig Approval

ESig Approval

ESig Approval

ESig Approval

ESig Approval

ESig Approval

Signature Page for VV-RIM-00078988 v1.0 Approved

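### SAP item 5 drops the pooled on-evinacumab model for seven lipids drawn at the same visits as TG, on a non-convergence reason that does not fit them

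*SAP*

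**What the plan says.** Protocol 10.4.3.2 sets the general rule: "Continuous secondary and exploratory endpoints will be analyzed similarly to the primary endpoint, except PP will not be computed". The feature of the primary analysis that matters here is pooling. SAP 5.7.1 keeps it for TG: "Note that study visits will be adjusted to start of evinacumab in order to pool data from both randomized groups of patients for this analysis". The TG baseline is the mean of three log values, taken at day -28, day -14 and week 0 for evinacumab-first patients and at weeks 6, 8 and 12 for placebo-first patients. The model uses an unstructured covariance.

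SAP 1.2.4 item 5 withdraws the general rule. It says that the rule "was deleted since for some continuous variables MMRM model may not converge due to the small number of visits/observations", and it points to SAP 5.7.2 (lipids) and 5.9 to 5.12 for the replacements.

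SAP 5.7.2 replaces the model with descriptive summaries and visit-by-visit tests: "For the evinacumab treated group, within-patient testing of endpoints with a non-normal distribution will use the Wilcoxon signed-rank test", or a paired t-test where the data are normal. The p-values are descriptive, and no confidence interval is planned for these lipids. Single-blind lipid data receive descriptive statistics only. Under SAP 4.7 the baseline for efficacy variables other than TG stays at the last value before double-blind dosing, in both periods.

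On the visit schedule, the footnotes in SAP 10.4.1 put the panel on one row: "Lipids and lipoproteins, total cholesterol, LDL-C, HDL-C, TG, APOB, APOA1, and Lp(a) will be measured except at visit 1 and 1b". SAP 4.7 calculates non-HDL-C from total-C and HDL-C.

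**The concern.** Item 5 gives a reason that by its own words concerns some variables, and applies it to all of them. Where the reason fails, information is given up for nothing in return.

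The design gives evinacumab to every patient who completes the double-blind period. Protocol 3.2.1 says that the single-blind period is there so that a treatment effect can be analysed in patients randomised to placebo. For TG the SAP uses that feature. For the rest of the main lipid panel, placebo-first patients' values on evinacumab appear only in descriptive single-blind tables. Their changes there are measured from a baseline taken before 12 weeks of placebo, not from their own values just before evinacumab. At stake is the precision of the on-drug lipid estimates in a trial of at most about 50 patients, and their comparability with the TG estimate.

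**Working it through.** **Does the reason fit?** The schedule of events (Protocol Table 1, SAP 10.4) gives these lipid visits after the start of evinacumab:

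| Group | On-drug weeks with a lipid draw |
|---|---|
| Evinacumab-first | 2, 4, 6, 8, 12, 16, 20, 24 |
| Placebo-first (study weeks 16, 20, 24) | 4, 8, 12 |

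Over the first 12 weeks on drug the aligned model has five post-baseline visits (2, 4, 6, 8, 12). An unstructured matrix then has 5 × 6 / 2 = 15 covariance parameters. The count is 15 for TG, where the SAP keeps the model, and 15 for each of the seven lipids, where it does not. Patients and scheduled draws are the same. The SAP also excludes TG values that are non-fasting or lack a fasting status, and states no such exclusion for the other lipids. A shortage of visits or observations therefore does not separate these lipids from TG.

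**What share of the data is left out?** Allocation is 2:1. The SAP does not define the evinacumab-treated group. I read it as the double-blind evinacumab arm, because 5.7.2 summarises by treatment group and makes the single-blind period descriptive. On that reading, placebo-first patients supply:

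- patients ever on evinacumab: 1/3 = 33%
- values at the shared on-drug weeks 4, 8 and 12: 1/3 = 33%
- all lipid values in the first 12 weeks on drug: (3 × 1) / (5 × 2 + 3 × 1) = 3/13 = 23%
- all on-drug lipid values to week 24: (3 × 1) / (8 × 2 + 3 × 1) = 3/19 = 16%

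**The plan's own precision figure.** SAP 2.2 uses a log-scale SD of 0.5 for TG and a 90% CI around a 40% reduction. The limits are 1 − 0.6 × exp(± t × 0.5/√N).

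- N = 10: half-width 0.2898, giving 19.8% to 55.1% (stated: 20% to 55%)
- N = 12: half-width 0.2592, giving 22.2% to 53.7% (stated: 22% to 54%)

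Both reproduce.

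**The loss at a shared visit.** With equal SD of change in both groups and no dropout, the SE ratio of evinacumab arm alone to pooled is √(N pooled / N arm), whatever the SD:

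- 50 randomised: √(50/33) = 1.23
- 30 randomised: √(30/20) = 1.22

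Suppose instead that a fifth of the placebo-first patients give no on-drug value and no evinacumab-first patient is lost. With 30 randomised, the ratio is √(28/20) = 1.18.

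On the plan's TG scale, with its 16 + 8 = 24 evaluable patients:

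- pooled, N = 24: half-width 0.1749, 90% CI 28.5% to 49.6%
- evinacumab arm alone, N = 16: half-width 0.2191, 90% CI 25.3% to 51.8%

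The half-width ratio is 0.2191/0.1749 = 1.25, slightly above the SE ratio because of the t quantile. The documents give no SD for the other lipids, so these intervals only illustrate the scale. The SE ratio does not depend on the SD.

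**The case against.** The strongest reply is that the change is openly declared with a reason, that the trial is exploratory without type-I error control, and that reporting randomised double-blind data apart from single-blind data is a defensible choice. Placebo-first patients do not vanish: SAP 5.7.2 summarises their single-blind lipids by prior treatment. What they leave is a test whose p-value is descriptive, and even that depends on how an undefined term is read. All of this stands and limits the weight of the point. It does not make the non-convergence reason fit lipids that share TG's schedule. If 5.7.2 does mean to include switchers, it must say so and give them a pre-switch baseline.

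Four stronger readings are tempting, and the documents do not support them.

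- A reader might infer that item 5 strips the model from every continuous secondary endpoint. It does not. For TG, SAP 5.7.1 still promises that "The point estimates of TG percent changes between the placebo period and each observation week will be calculated" by the pooled MMRM over 12 weeks on drug, and 5.7.1.1 extends the model to cohorts. The seven lipids are exploratory or lipid-panel variables, not named secondary endpoints.
- A reader might infer that the secondary TG objective ("To determine the percent change from baseline in TG levels following 2 to 24 weeks of repeated IV doses of evinacumab overall") loses its model after week 12 through item 5. Protocol 10.4.3.2 itself planned only optional summary statistics beyond week 12, in patients randomised to evinacumab. The SAP wording that "a combined summary including both the DBTP and SBTP assessments may be considered" is close to that.
- A reader might extend the point to PET. Protocol 10.4.3.2 confined the PET comparisons to the double-blind period, so no pooled on-drug PET analysis was removed.
- A reader might say that a third of the on-drug data is lost. The third refers to patients and to values at shared visits; the other shares are 23% and 16%, as shown above.

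**Conclusion.** The point holds for seven lipids over the first 12 weeks of evinacumab. The stated reason does not apply to them, and the replacement is less precise than the protocol's analysis: the SE at on-drug weeks 4, 8 and 12 is about 22% to 23% larger. That figure assumes equal SD of change in the two groups, no dropout, and that the tested group is the double-blind evinacumab arm. At on-drug weeks 2 and 6 placebo-first patients have no draw, so pooling adds no direct observations there. The consequence is lost precision and a baseline inconsistent with the TG analysis, not bias in the primary result, which item 5 leaves untouched.

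**What to change.** 1. In SAP 1.2.4 item 5, limit the deletion to sparsely measured variables, such as HbA1c, insulin, C-peptide, Apo C2, Apo CIII, Apo A5, NEFA and post-heparin LPL activity.
2. In SAP 5.7.2, fit the primary-type log-scale MMRM to total-C, LDL-C, HDL-C, non-HDL-C, Apo B, Apo A1 and Lp(a) over the first 12 weeks of evinacumab, pooling both randomised groups, and report the LS mean ratio with its CI.
3. State the baseline for placebo-first patients in that model: either the pre-switch values at weeks 6, 8 and 12, as for TG, or the week-12 pre-dose value. The SAP sets a pre-switch baseline only for TG, so this is a new definition and not just a re-run of existing code.
4. Define the evinacumab-treated group wherever the within-patient tests are kept.
5. Keep the descriptive tables as the stated fallback if a model fails.

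The cost is some extra programming and a possible convergence failure, which the fallback covers.

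Optional, as an addition and not as repair of item 5: for TG at on-drug weeks 16 to 24, report a geometric mean ratio with CI in evinacumab-first patients. A simple paired log-scale analysis would do. An unstructured MMRM over all eight visits has 8 × 9 / 2 = 36 covariance parameters, so that route needs a named fallback covariance.

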1.2.5. Revision History for Statistical Analysis Plan Amendments

This is the first version of Statistical Analysis Plan (SAP).

2. INVESTIGATION PLAN

2.1. Study Design and Randomization

This is a phase 2, randomized, placebo-controlled, study designed to evaluate the efficacy and safety of repeated doses of evinacumab in adult patients with severe HTG. Up to approximately 50 patients will be enrolled, randomized 2:1 (evinacumab:placebo) to receive evinacumab 15 mg/kg IV every 4 weeks (Q4W) or matching placebo IV Q4W for the 12-week double-blind treatment period (DBTP). After completion of the DBTP, all patients will enter a 12-week single-blind treatment period (SBTP) and receive open-label evinacumab 15 mg/kg IV Q4W. Investigators, Regeneron Study Director, Medical Monitor, Study Monitor, and any other Regeneron and contract research organization (CRO) personnel who are in regular contact with the study site will be blinded to treatment assignment during the double-blind treatment period of

the study and blinded to blood lipid measurements during the double-blind and single-blind treatment periods. After SBTP, all patients will undergo a 24-week follow-up after the last dose of study treatment.

The following cohorts will be enrolled based upon information (or lack of information) on genotype in the patient's medical history at screening:

1. Cohort 1: FCS due to complete LPL deficiency. Approximately 6 to 9 patients will be enrolled. This cohort consists of patients:
 - with known homozygous or compound heterozygous null LPL, GPIHBP1, or APOC2 LOF mutations
2. Cohort 2: Multifactorial chylomicronemia with partial LPL deficiency. Approximately 9 to 12 patients will be enrolled. This cohort consists of patients:
 - with known heterozygous null LPL, GPIHBP1, or APOC2 LOF mutations, or
 - with uncharacterized or known non-null LOF LPL pathway gene mutations (LPL, apoC2, apoA5, LMF1 and GPIHBP1)
3. Cohort 3: Multifactorial chylomicronemia. Approximately 15 to 27 patients will be enrolled. This cohort consists of patients not included in cohorts 1 or 2 above:
 - with other monogenic or polygenic causes of sHTG (eg, CGKR, CREB3L3, E2/E2 dysbetalipoproteinemia), or
 - without genotype information

